8.1. Definition of an AE

Any untoward medical occurrence in a subject or clinical investigation subject administered a pharmaceutical product and which does not necessarily have to have a causal relationship with this treatment.

An AE can therefore be any unfavorable and unintended sign (including an abnormal laboratory finding), symptom, or disease (new or exacerbated) temporally associated with the use of a medicinal product, whether or not considered related to the medicinal product.

8.2. Definition of an AESI

The following events will be considered AESI and must be reported to Intuvigilance (same procedure as SAE).

Skin Lesions (regardless of its severity)

A dermatologist consultation should be scheduled to evaluate the type of lesion, its severity and etiology. An anonymized medical report shall be provided.

Headaches

Headaches are frequently reported by patients dosed with ABX464. Abivax follows closely, by means of individual adapted questionnaire, provided in Appendix #4, this AE in specific situations (i.e. headache lasting longer than 72 hours AND not resolved by standard painkillers).

Anemia

Some degree of anemia was found in the 9-month marmoset study with ABX464-N-Glu. Although it has not been reproduced clinically, Abivax performs surveillance for anemia by means of regular determination of hemoglobin and hematocrit levels. Anemia defined as Hb drop > 2 g/dL from baseline or Hb < 8g/dL will be reported as AESI.

Hepatic enzymes

ABX464 showed liver findings in some toxicological studies, hence attention is paid to identification of liver enzymes elevations in subjects. No human predictors of hepatotoxicity for ABX464 or its metabolite, ABX464-N-Glu, have been identified. Based upon preclinical and clinical available data, a DILIsym evaluation of ABX464 was conducted and concluded that there was no risk of DILI in these patients. A signal detection analysis of ALT/AST changes in subjects treated with ABX464 did not reveal any meaningful variation of the mean ALT/AST measurement throughout treatment nor an increased incidence of any liver function tests (LFTs). Sporadic cases of isolated alkaline phosphatase increase have been reported in patients dosed with ABX464.

A specific liver function monitoring plan is implemented in all clinical studies (see Section 5.3.10 and Section 7.2) during the course of treatment and a measurement of LFTs 4 weeks after treatment interruption (during End of Study visit). The LFTs should, as per the clinical protocols, include at least the determination of the liver transaminases (ALT/AST), gamma-glutamyl transferase (GGT), alkaline phosphatase and total bilirubin. Specifically, an increase $\geq 3.0 \times$ ULN in liver transaminases (AST/SGOT and/or ALT/SGPT) or an increase $\geq 2.0 \times$ ULN in total bilirubin without initial findings of cholestasis (elevated alkaline phosphatase) will be reported as AESI.

Severe (grade ≥ 3) infections and opportunistic infections

Immunosuppression has been observed during the 9-month cynomolgus monkey study with ABX464-N-Glu dosed directly by oral gavage. Therefore, serious (grade 3) infections and opportunistic infections due to bacterial,

mycobacterial, invasive fungal, viral, or parasitic organisms (including aspergillosis, blastomycosis, candidiasis, coccidioidomycosis, histoplasmosis, legionellosis, listeriosis, pneumocystosis, and tuberculosis) will be reported as AESIs. Subjects will be monitored for the development of signs and symptoms of infection during treatment with ABX464. ABX464 will be discontinued if a subject develops a severe (grade 3 or higher) infection, a severe (grade 3 or higher) opportunistic infection, or sepsis.

Acute pancreatic adverse events

Cases of transient increase in lipase serum levels have been observed in ABX464 clinical studies in ulcerative colitis patients as well as in patients with COVID-19 infection (blinded placebo/ABX464 treatment). Therefore, lipase and amylase will be monitored in the clinical studies. An elevation of serum lipase and/or amylase at least three times greater than the upper limit of normal will be reported as AESI and a workup for a diagnosis of pancreatitis will be performed according to the Atlanta criteria for the definition of acute pancreatitis.

Definition of diagnosis of acute pancreatitis^[10]

The diagnosis of acute pancreatitis requires two of the following three features:

- Abdominal pain consistent with acute pancreatitis (acute onset of a persistent, severe, epigastric pain often radiating to the back);
- Serum lipase activity (or amylase activity) at least three times greater than the upper limit of normal; and
- Characteristic findings of acute pancreatitis on contrast-enhanced computed tomography (CECT) and less commonly magnetic resonance imaging or transabdominal ultrasonography.

If abdominal pain suggests strongly that acute pancreatitis is present, but the serum amylase and/or lipase activity is less than three times the upper limit of normal, as may be the case with delayed presentation, imaging will be required to confirm the diagnosis. The CECT will be planned and performed locally in that case.

If the diagnosis of acute pancreatitis is established by abdominal pain and by increases in the serum pancreatic enzyme activities, a CECT is not usually required for diagnosis in the emergency room or on admission to the hospital.

Malignancies including Non-Melanoma Skin Cancers

Despite a lack/paucity of reported events in non-clinical and clinical trials, a potential impact on both innate and adaptive immune responses and the novel mechanism of action, could be a concern with regards to malignancies, mainly in the long-term. Therefore, all malignancies including non-melanoma skin cancers will be reported as an AESI.

Cardiac Fibrosis:

Two cases of cardiac fibrosis, likely associated with the marmoset wasting syndrome^[11], have been observed in a 9-month study with marmoset monkeys exposed to high doses of ABX464-N-Glucuronide. These findings were considered to be spontaneous. A review of the safety database for ABX464 has revealed no changes in troponin level compared with placebo or any increased reporting of cardiovascular adverse events compared with placebo. However, the following cardiac monitoring will be performed in this study:

Additional cardiac Laboratory monitoring procedures will include:

1. Monitoring of AST, Troponin and creatinine phosphokinase (CPK) blood levels at each study visit, including baseline visit plus the End of Study Visit
2. Monitoring of N-terminal pro b-type natriuretic peptide (NT-proBNP) blood levels every 6 months plus at the End of Study Visit.

A relative change of more than 20% from baseline values in cardiac laboratory parameters will be reported as an AESI.

Two-dimensional echocardiography with local evaluation will be performed every 6 months.

An independent Cardiovascular Safety Committee (ICVSC) will evaluate cardiac AESIs, treatment emergent echocardiographic findings, and treatment emergent changes of cardiac safety biomarkers (as detailed above).

The following treatment emergent adverse events (TEAEs) will also be categorized as Cardiac AESI:

Under the Cardiac SOC:

- Aortic valve disease
- Asystole

- Atrial fibrillation
- Atrial flutter
- 3rd degree AV block (AV block complete)
- Cardiac arrest
- Chest pain – cardiac
- Heart failure
- Left ventricular systolic dysfunction
- Mitral valve disease
- Mobitz (type) II atrioventricular block (type 2, 2nd degree AV block)
- Myocardial infarction
- Myocarditis
- Pericardial effusion
- Pericardial tamponade
- Pericarditis
- Pulmonary valve disease
- Restrictive cardiomyopathy
- Right ventricular dysfunction
- Sick sinus syndrome
- Tricuspid valve disease
- Ventricular fibrillation
- Ventricular tachycardia

8.3. Definition of a SAE

A serious adverse event (experience) or reaction is any untoward medical occurrence that, at any dose:

- a) Results in death

NOTE: Death is an outcome of an AE, and not an AE in itself. Event which led to death should be recorded with fatal outcome.

- b) Is life-threatening

NOTE: The term 'life-threatening' in the definition of 'serious' refers to an event in which the subject was at risk of death at the time of the event. It does not refer to an event, which hypothetically might have caused death, if it were more severe.

- c) Requires hospitalization or prolongation of existing hospitalization

NOTE: In general, hospitalization means that the subject has been detained (usually involving at least an overnight stay) at the hospital or emergency ward for observation and/or treatment that would not have been appropriate in the physician's office or out-patient setting. Complications that occur during hospitalization are AEs. If a complication prolongs hospitalization or fulfills any other serious criteria, the event is serious. When in doubt as to whether "hospitalization" occurred, or was necessary, the AE should be considered serious.

Hospitalization for elective treatment of a pre-existing condition that did not worsen after informed consent was given is not considered an AE.

- d) Results in persistent or significant disability/incapacity,

NOTE: The term disability means a substantial disruption of a person's ability to conduct normal life functions. This definition is not intended to include experiences of relatively minor medical significance such as uncomplicated headache, nausea, vomiting, diarrhea, influenza, and accidental trauma (e.g. sprained ankle) which may interfere or prevent everyday life functions but do not constitute a substantial disruption.

- e) Is a congenital anomaly/birth defect

- f) Is another medically important condition: This refers to an AE that may not be immediately life-threatening or results in death or hospitalization but may jeopardize the subject or may require intervention to prevent one of the outcomes listed above. Based on medical and scientific judgment this should usually be considered serious.

If there is any doubt about whether or not an AE is serious, the investigator should contact the sponsor.

8.3.1. Events and/or Outcomes Not Qualifying as SAEs

Any hospitalization, or prolongation of hospitalization due to the circumstances listed below, will not be reported as SAE:

- planned medical/surgical procedure;
- planned medical/surgical admission (planned prior to entry into study, appropriate documentation required), for the disease under study;
- Administrative or social reasons (e.g. lack of housing, economic inadequacy, care-giver respite, family circumstances).

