2.4. Secondary Endpoints

The secondary endpoints of this study are:

- The change from Day 0 in Total Mayo Score.
- The change from Day 0 in Partial Mayo Score.
- The time to UC worsening.
- The change from Day 0 in fecal calprotectin, CRP levels and ESR.
- The scores and changes from Day 0 in SF-36 Questionnaire scores.
- The miR-124 expression at month 12, month 36 and month 48.
- The number of incidences of treatment-emergent serious adverse events.
- The number of incidences of treatment-emergent adverse events of special interest.
- The number of incidences of adverse events leading to investigational product discontinuation.
- The number of incidences of specific laboratory abnormalities.
- Percentage of subjects reaching clinical remission at M12, M36, and M48.
- Percentage of subjects reaching clinical response at M12, M36, and M48.
- Percentage of subjects reaching endoscopic improvement at M12, M36, and M48.
- Percentage of subjects reaching endoscopic remission at M12, M36, and M48.
- Percentage of subjects reaching corticosteroid-free clinical remission at M12, M36, and M48.

The echocardiography secondary endpoints^[9] are:

- Absolute (%) change-from-previous echocardiogram of Left ventricle Ejection Fraction (LVEF) as measured by 2-dimensional echocardiography
- Number of subjects with a clinically relevant reduction (change-from-previous echocardiogram) of LVEF, defined as by > 10% reduction (absolute percentage points) to a value < 50%

- Absolute (%) change in Global Longitudinal Strain (GLS) from-previous echocardiogram
- Number of subjects with a relative percentage reduction in GLS by > 15% from the previous value
- Number of subjects with a reduction of LVEF > 10% (absolute percentage points) to a value $\geq 50\%$ with an accompanying fall in GLS > 15%
- Number of subjects with reduction in LVEF by > 10% (absolute percentage points) to a value $\geq 50\%$
- Changes from previous echocardiography of other echocardiographic parameters as described in a standard protocol, including 2-dimensional volumes, RV size and systolic function and valve function.

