3.1.2. Data Safety Monitoring Board – Independent Cardiovascular Safety Committee (ICVSC)

An independent Data Safety Monitoring Board (DSMB), with expertise and experience in the pathology, and without direct involvement in the conduct of the trial, will be set up specifically to guarantee effective protection of subjects, ensure the ethical conduct of the trial, benefit/risk ratio of the trial, and to ensure the independent review of the scientific results during the trial and at the end of the trial.

The DSMB will meet on a monthly basis until December 2019 and then quarterly from January 2020 onwards. Besides, the DSMB may recommend the early termination of the trial at any time if an unacceptable toxicity occurs.

In addition, DSMB will be review all potential causally related Serious Adverse Events within 7 days of the initial report.

The DSMB has only a consultative role; it will inform the sponsor who will decide whether the DSMB recommendation will be followed. A DSMB charter must be available upon submission of the trial (initial protocol) to the respective competent authorities.

An Independent Cardiovascular Safety Committee (ICVSC), comprised of 3 cardiologists with experience from drug development, will be formed as detailed in the Charter. The ICVSC will be responsible for an on-going evaluation of cardiac adverse events of special interest (Cardiac AESIs), for treatment emergent echocardiographic findings, and for treatment emergent changes of cardiac safety biomarkers (as detailed above). The ICVSC will review cardiac adverse events on an on-going basis, meet regularly and provide recommendations to Sponsor and DSMB regarding study procedures and conduct.

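### Protocol 8.3.1 exempts planned procedures from SAE reporting without the limits set in 8.3(c), so an on-treatment event managed by a scheduled admission may go unreported as an SAE

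*Protocol*

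**What the plan says.** Protocol Section 8.3, criterion (c), makes an untoward occurrence serious if it "Requires hospitalization or prolongation of existing hospitalization". The note to that criterion carves out one case: "Hospitalization for elective treatment of a pre-existing condition that did not worsen after informed consent was given is not considered an AE". Criterion (f) is a separate ground, for an event that "may jeopardize the subject or may require intervention to prevent one of the outcomes listed above".

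Section 8.3.1 then lists exceptions under the lead-in "Any hospitalization, or prolongation of hospitalization due to the circumstances listed below, will not be reported as SAE". The first is "planned medical/surgical procedure", with nothing added. The second is "planned medical/surgical admission (planned prior to entry into study, appropriate documentation required), for the disease under study". The third covers administrative or social reasons.

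Three things depend on the classification. Protocol Section 2.4 has the secondary endpoint "The number of incidences of treatment-emergent serious adverse events". Protocol Section 3.1.2 has the DSMB review "all potential causally related Serious Adverse Events within 7 days of the initial report". SAP Section 11.6.1 plans a table of serious TEAEs and a listing of SAEs. The SAP sets no seriousness rule of its own and refers the reader to protocol Section 8.

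**The concern.** The protocol contains three statements on elective hospitalisation, and two of them carry limits. The note to 8.3(c) requires a pre-existing condition that has not worsened. The second bullet of 8.3.1 requires planning before entry, documentation, and the disease under study as the reason. The first bullet requires only that the procedure be planned. An operation that becomes necessary because of something that happened on ABX464, and is then booked for a date, is planned in the ordinary sense of the word.

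The study treats patients for 48 months, and its primary objective is long-term safety. Over that time a new condition can well be managed by a booked admission rather than an emergency one. If sites apply the first bullet as it stands, such events can drop out of the serious category. The error has one direction, since the bullet can only remove SAEs. Hospitalisation is also the most objective of the seriousness criteria likely to apply to these events; criterion (f), the main alternative, rests on judgement.

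**Working it through.** The documents give no figure to reproduce, so the check sets the rules side by side and applies them to one case.

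| Rule | Planned before consent or entry? | Documentation? | Limit on the condition? |
|---|---|---|---|
| Note to 8.3(c) | Condition must pre-date consent | Not stated | Pre-existing and not worsened |
| 8.3.1, second bullet | Yes, before entry | Yes | Disease under study |
| 8.3.1, first bullet | Not stated | Not stated | Not stated |

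Test case: a condition that is neither UC nor on the AESI list first arises during treatment. It needs surgery, and the patient is admitted on a booked date.

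1. Under 8.3(c) the event requires hospitalisation, so it is serious. The note does not help, because the condition is not pre-existing.
2. The second bullet of 8.3.1 does not apply: the admission was not planned before entry and is not for UC.
3. The first bullet of 8.3.1 applies on its wording: the hospitalisation is due to a planned procedure and is not reported as an SAE.
4. Steps 1 and 3 give opposite answers, and neither document says which prevails.
5. The first bullet removes the hospitalisation ground only. Criteria (a), (b), (d), (e) and (f) still apply, so the event is an SAE if the investigator judges that one of them is met. If none is judged to be met, it remains a non-serious AE.

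Consequence by output:

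- Count of TEAEs (primary endpoint, protocol Section 2.3): unchanged, because the event is still recorded as an AE.
- Count of serious TEAEs, serious-TEAE table, SAE listing: one event fewer.
- DSMB 7-day review: missed if the event was potentially causally related.
- 24-hour report (protocol Sections 8.5 and 8.7): missed, because the event is neither an SAE nor an AESI.

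If the event is an AESI instead, such as a malignancy or a listed cardiac event, protocol Section 8.2 sends it by the SAE procedure and the 24-hour report is kept. AESI status does not make the event serious, so the second and third items still apply.

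Size per patient: protocol Section 1.3 gives 22 patients enrolled, 15 previously on ABX464 and 7 on placebo. If the missed event is a patient's only serious TEAE, the patient rate falls by 1/22 = 4.5 percentage points in the total column. For example, 2/22 = 9.1% would be reported as 1/22 = 4.5%. In the two group columns the step is 1/15 = 6.7 or 1/7 = 14.3 points.

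**The case against.** The strongest reply is that the protocol, read as a whole, already catches most events that matter.

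- Criterion (f) is a natural home for an event that needs an operation, and Section 8.3 says such events should usually be considered serious.
- Section 8.3 has tie-breakers: doubt about whether hospitalisation occurred or was necessary counts as serious, and any doubt about seriousness goes to the sponsor.
- Malignancies and the listed cardiac conditions are AESIs with a 24-hour report and their own table, and cardiac AESIs are also reviewed by the ICVSC.
- Surgery for worsening UC is governed by a different rule, at the start of protocol Section 8, which keeps disease progression out of the AE pages.

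Much of this stands. A reader might infer that an operation scheduled on study simply is not an SAE. The documents do not support that, because 8.3.1 removes one ground of several. A reader might also infer that the first bullet takes precedence over 8.3 and over the second bullet. No text says so, and on that reading the limits in the second bullet would do almost no work. Nor do tumour or cardiac admissions escape expedited reporting; the AESI route covers malignancies and the listed cardiac conditions.

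What the reply does not remove is the conflict itself. The tie-breakers work only where the investigator is in doubt, and an unqualified bullet gives no reason for doubt. Criterion (f) puts judgement in place of the objective criterion. AESI reporting does not put an event into the serious-TEAE count, the SAE listing or the DSMB's 7-day review. A new condition that is neither UC nor an AESI has no second route at all.

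**Conclusion.** The first bullet of 8.3.1 conflicts with 8.3(c), and the two must be reconciled. The effect is a possible undercount, in one direction, of the serious-TEAE secondary endpoint, the SAE table and listing, and the DSMB's 7-day review of related SAEs. Loss of the 24-hour report is confined to events that are not AESIs. The primary endpoint is not affected.

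Each patient misclassified costs 4.5 percentage points on the SAE patient rate, assuming 22 patients in the denominator and no other serious TEAE in that patient. How many patients this concerns cannot be derived from the documents. It is tempting to apply an assumed admission rate to the largest possible exposure, 22 x 4 = 88 patient-years: 1 to 5 planned admissions per 100 patient-years would give 0.9 to 4.4. That range does not measure the undercount. The rate is not in the documents, it includes admissions that are properly exempt or serious on other grounds, and 88 patient-years ignores early withdrawals. The point rests on the text and needs no such figure. A correction is worth making because the conflict touches a named safety endpoint and costs little to remove.

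**What to change.** Limit the first bullet of 8.3.1 to procedures planned before informed consent, with documentation, for a pre-existing condition that has not worsened since consent. Add that where a new or worsened condition leads to a planned admission, the underlying event is assessed for seriousness under 8.3(c). The reportable item should be the event, since 8.3 defines an SAE as an untoward occurrence and not as the admission.

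Before database lock, cross-match the procedures in SAP Listing 16.2.10 that are marked as given for an adverse event with events marked non-serious in Listing 16.2.7. Then ask the sites whether an admission took place. The query is needed because Listing 16.2.10 has no hospitalisation field, and the check finds only procedures that were recorded and linked to an AE. SAP Section 1.1 says that treatment was still ongoing when the plan was written, so this could be done before lock.

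The cost is one reworded bullet, one added sentence, a memo to sites and a few queries. The reported SAE count may rise slightly.

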8.4. Events or Outcomes Qualifying as AEs or SAEs

8.4.1. Clinical laboratory parameters

Abnormal laboratory findings (e.g., clinical chemistry, hematology) or other abnormal assessments (e.g. vital signs) that are judged by the investigator as **clinically significant** will be recorded as AEs or SAEs if they meet the definitions of sections 8.1 and 8.2 respectively. Clinically significant abnormal laboratory findings or other abnormal assessments that are detected during the study or are present at informed consent and significantly worsen during the study will be reported as AEs or SAEs. Clinically significant abnormal laboratory findings or other abnormal assessments that are associated with the disease being studied, and are present at the start of the study but do not worsen, will **not** be reported as AEs or SAEs. However, if these findings or assessments are judged by the investigator to be more severe than expected considering the subject's condition, then they may be reported as AEs or SAEs.

